9.3 Adverse Events Post Study

All unresolved adverse events at the conclusion of the dosing period should be followed by the investigator until the event is resolved, the participant is lost to follow-up, or the adverse event is otherwise explained. At the last scheduled contact, the study staff should instruct each participant to report any subsequent event(s) that the participant, or the participant's personal physician, believes might reasonably be related to participation in this study.

9.4 Adverse Events Assessment and Recording

At each contact with the participant, the investigator or study staff will assess for information on adverse events and review all self-reported AE's via the study portal. Information surrounding adverse events should be recorded in the study portal. Related signs, symptoms, and abnormal diagnostic procedures results should be recorded in the study portal and grouped under one diagnosis as applicable.

Adverse events can be spontaneously reported or elicited during open-ended questioning. Adverse events will be measured and graded in accordance with the document entitled *Division of AIDS (DAIDs) Table for Grading the Severity of Adult and Pediatric Adverse Events, Corrected Version 2.1, July 2017* issued by the US Department of Health and Human Services. The clinical course of each event should be followed until resolution, stabilization, or until it has been determined that the study treatment or participation is not the cause. Serious adverse events that are still ongoing at the end of the study period must be followed up to determine the final outcome. Any serious adverse event that occurs after the study period and considered to be at least possibly related to the study treatment or study participation should be recorded and reported immediately.

9.4.1 Relationship to Study Drug

The causal relationship can be one of the following:

- Related: There is a possible, probable or definite causal relationship between study drug administration and the AE
- Not related: There is evidence suggesting a causal relationship to something other than the study drug.

9.5 Abnormal Laboratory Values

This trial does not require any safety laboratory assessments. However, in the event a participant has a standard of care lab completed which are self-reported and meet the DAIDS criteria for Grade 2 or greater, and cannot be attributed to another cause, study drug should be held and or reduced in accordance with section 8 above.

9.6 Diagnosis vs. Signs and Symptoms

If known at the time of reporting, a diagnosis should be reported rather than individual signs and symptoms (e.g., record only liver failure or hepatitis rather than jaundice, asterixis, and elevated transaminases). However, if a constellation of signs and/or symptoms cannot be medically characterized as a single diagnosis or syndrome at the time of reporting, it is ok to report the information that is currently available. If a diagnosis is subsequently established, it should be reported as follow-up information.

9.7 Preexisting Medical Conditions

A preexisting medical condition is one that is present at the start of the study. Such conditions should be reported as medical and surgical history. A preexisting medical condition should be re-assessed throughout the trial and reported as an AE or SAE only if the frequency, severity, or character of the condition worsens during the study. When reporting such events, it is important to convey the concept that the preexisting condition has changed by including applicable descriptors (e.g., “more frequent headaches”).

10.0 SERIOUS ADVERSE EVENTS

A serious adverse event is any AE that is:

- fatal
- life-threatening
- requires or prolongs hospital stay
- results in persistent or significant disability or incapacity
- a congenital anomaly or birth defect
- a suspected transmission of an infectious agent (e.g., pathogenic or nonpathogenic) via the study drug
- an important medical event
- All Serious Adverse Events (SAEs) that occur following the participant’s written consent to participate in the study must be reported, whether related or not related to study drug. If applicable, SAEs must be collected that relate to any later protocol-specified procedure.
- Following the participant’s written consent to participate in the study, all SAEs, whether related or not related to study drug, are collected, including those thought to be associated with protocol-specified procedures. The investigator should report any SAE occurring after these aforementioned time periods, which is believed to be related to study drug or protocol-specified procedure.
- An SAE report should be completed for any event where doubt exists regarding its seriousness;
- If the investigator believes that an SAE is not related to study drug but is potentially related to the conditions of the study (such as withdrawal of previous therapy or a complication of a study procedure), the relationship should be specified in the narrative section of the SAE Report Form.

All SAEs should be followed to resolution or stabilization. Serious adverse events that are ongoing at the end of the study period must be followed to determine the outcome. Any serious adverse event that occurs after the study period and is at least possibly related to the study treatment or study participation should be recorded and reported immediately to the Medical Monitor and the IRB per the IRB reporting guidelines.

PATCH 2 & 3 TRIAL

All adverse events that do not meet any of the criteria for serious should be regarded as non-serious adverse events.

10.1 Important Medical Event

Important medical events are those that may not be immediately life threatening but are clearly of major clinical significance. They may jeopardize the participant and may require intervention to prevent one of the other serious outcomes noted above. For example, drug overdose or abuse, a seizure that did not result in in-patient hospitalization, or intensive treatment of bronchospasm in an emergency department would typically be considered serious.

10.2 Hospitalization, Prolonged Hospitalization or Surgery

Any adverse event that results in hospitalization or prolonged hospitalization should be documented and reported as a serious adverse event unless specifically instructed otherwise in this protocol. Any condition responsible for surgery should be documented as an adverse event if the condition meets the criteria for an adverse event.

Neither the condition, hospitalization, prolonged hospitalization, nor surgery are reported as an adverse event in the following circumstances:

- Hospitalization or prolonged hospitalization for diagnostic or elective surgical procedures for a preexisting condition. Surgery should not be reported as an outcome of an adverse event if the purpose of the surgery was elective or diagnostic and the outcome was uneventful.
- Hospitalization or prolonged hospitalization required to allow efficacy measurement for the study.
- Hospitalization or prolonged hospitalization for therapy of the target disease of the study, unless it is a worsening or increase in frequency of hospital admissions as judged by the clinical investigator.

Expected adverse events are those adverse events that are listed or characterized in the Package Insert or current Investigator Brochure.

Unexpected adverse events are those not listed in the Package Insert (P.I.) or current Investigator Brochure (I.B.) or not identified. This includes adverse events for which the specificity or severity is not consistent with the description in the P.I. or I.B. For example, under this definition, hepatic necrosis would be unexpected if the P.I. or I.B. only referred to elevated hepatic enzymes or hepatitis.

10.3 Deaths

All deaths that occur during the protocol-specified AE reporting period (see Section 12.1), regardless of attribution, will be reported to the appropriate parties. When recording a death, the event or condition that caused or contributed to the fatal outcome should be reported as the single medical concept. If the cause of death is unknown and cannot be ascertained at the time of reporting, report "Unexplained Death".

10.4 Pregnancy

If a female subject becomes pregnant while receiving investigational therapy or within 120 days after the last dose of study drug, the investigator must immediately notify the Sponsor in accordance with SAE reporting guidelines. Follow-up to obtain the outcome of the pregnancy should also occur. Abortion, whether accidental, therapeutic, or spontaneous, should always be classified as serious, and expeditiously reported as an SAE. Similarly, details of the birth, and the presence or absence of any congenital anomaly/birth defect or maternal and/or newborn complications in a child born to a female subject exposed to the study drug should be reported as an SAE. Follow-up information regarding the course of the pregnancy, including perinatal and neonatal outcome and, where applicable, offspring information must be reported. In order for Sponsor or designee to

PATCH 2 & 3 TRIAL

collect any pregnancy surveillance information from the female partner must sign an informed consent form for disclosure of this information. Any pregnancy that occurs in a female partner of a male study participant should be reported. Information on this pregnancy will be collected on the Pregnancy Surveillance Form. In order for Sponsor or designee to collect any pregnancy surveillance information from the female partner, the female partner must sign an informed consent form for disclosure of this information.

11.0 IRB NOTIFICATION

The UHG IRB requires expedited reporting of those events related to study participation that are unforeseen and indicate that participants or others are at increased risk of harm. The IRB will not acknowledge safety reports or bulk adverse event submissions that do not meet the criteria outlined below. The IRB requires researchers to submit reports of the following problems within 10 working days from the time the investigator becomes aware of the event:

- Any adverse event (regardless of whether the event is serious or non-serious, on-site or off-site) that occurs any time during or after the research study, which in the opinion of the principal investigator is:

Unexpected (An event is “unexpected” when its specificity and severity are not accurately reflected in the protocol-related documents, such as the IRB-approved research protocol, any applicable investigator brochure, and the current IRB-approved informed consent document and other relevant sources of information, such as product labeling and package inserts.)

AND

Related to the research procedures (An event is “related to the research procedures” if in the opinion of the principal investigator or sponsor, the event was more likely than not to be caused by the research procedures.)

Deaths occurring for participants on-study and within 30 days of study drug administration that are considered unforeseen and indicates participants or others are at increased risk of harm (i.e. unexpected and probably/definitely related), must be reported to the IRB within 24 hours of notification.

Copies of each report and documentation of IRB notification and receipt will be kept in the Clinical Investigator’s study file.

For clinical drug trials, the following events are also reportable to the IRB:

- Any adverse experience that, even without detailed analysis, represents a serious unexpected adverse event that is rare in the absence of drug exposure (such as agranulocytosis, hepatic necrosis, Stevens-Johnson syndrome).
- Any adverse event that would cause the sponsor to modify the investigators brochure, protocol or informed consent form, or would prompt other action by the IRB to assure protection of human participants.
- Information that indicates a change to the risks or potential benefits of the research, in terms of severity or frequency. For example:
 - An interim analysis indicates that participants have a lower rate of response to treatment than initially expected.
 - Safety monitoring indicates that a particular side effect is more severe, or more frequent than initially expected.

PATCH 2 & 3 TRIAL

-- A paper is published from another study that shows that an arm of your research study is of no therapeutic value.

- Change in FDA safety labeling or withdrawal from marketing of a drug, device, or biologic used in a research protocol.
- Breach of confidentiality
- Change to the protocol taken without prior IRB review to eliminate apparent immediate hazard to a research participant.
- Incarceration of a participant when the research was not previously approved under Subpart C and the investigator believes it is in the best interest of the participant to remain on the study.
- Complaint of a participant when the complaint indicates unexpected risks, or the complaint cannot be resolved by the research team.
- Protocol violation (meaning an accidental or unintentional deviation from the IRB approved protocol) that in the opinion of the investigator placed one or more participants at increased risk or affects the rights or welfare of participants.

The IRB will accept other reports when the investigator is unsure whether the event should be reported, and the IRB will review such reports to determine whether the event meets the threshold for an unanticipated event presenting risk to the participant. Reports requiring IRB consideration or consultation are to be emailed to [name], Vice President, Human Research Affairs at UnitedHealth Group at [contact].

11.1 Reporting Process to IRB.

Principal Investigators are encouraged to submit reports of unanticipated problems posing risks to participants or others via a written report of the event (including a description of the event with information regarding its fulfillment of the above criteria, follow-up/resolution and need for revision to consent form and/or other study documentation) within 7 working days to the UnitedHealth Group Office of Human Research Affairs (OHRA). Participating sites should follow local, institutional guidelines on Event Reporting. For reportable deaths, the initial submission to the IRB may be made by contacting [name] at [contact].

This study is IND exempt and reporting to the FDA is voluntary using a MedWatch 3500 or via the FDA's website for voluntary reporting.

12.0 PARTICIPANT WITHDRAWAL

Each participant has the right to withdraw from the study at any time without prejudice. The investigators may discontinue any participant's participation for any reason, including adverse event or failure to comply with the protocol. Should a participant withdraw from the study, the reason(s) must be recorded within the study portal. Reasons for withdrawal include the following:

- Progression of Disease: Remove participant from study at the time progressive disease is documented.
- Extraordinary Medical Circumstance: If at any time the treating physician feels constraints of this protocol are detrimental to the participant's health the participant should be withdrawn.
- Participant's refusal to continue treatment: In this event, document the reason(s) for treatment refusal.
- Failure to comply with protocol (as judged by the investigator such as compliance below 80%, failure to maintain appointments, etc.).
- Delay in treatment > 7 days due to toxicity or ongoing toxicity \geq Grade 2 following two (2) dose reductions.

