9. Three times a week, participants will be called by clinical research coordinators to assess AEs and symptoms with all discussions well-documented. Clinical research coordinators may clinically escalate any medical determinations to Co-PI
10. After Day 14, which marks the end of the treatment period, participants will no longer be expected to continue self-reporting information into the study portal. Participant will undergo follow-up testing for COVID-19 at two additional time points. The first will be either day 15, 16 or 17, with the second on either on day 29, 30 or 31
11. If during active participation, the participant reports worsening of symptoms related to COVID-19 from baseline, this is reported to the PI for further clinical evaluation

Participant Procedure PATCH 3 (Sub-Study 2) (See study process flows)

1. Interested participants self-refer for study by completing online eligibility checklist on study portal (www.patchstudy.com)
2. Review inclusion and exclusion criteria:
 - Currently employed as a health care worker ([name]; Doctor of Osteopathic Medicine, DO; Nurse Practitioner, NP; Physician's Assistant, PA; and [name] or other members of the medical care team with significant COVID-19 exposure);
 - Asymptomatic and presumed negative for COVID-19 (no confirmatory testing conducted);
 - Scheduled for an average of >20 hours per week of clinical care over the next two months (or equivalent indicating at least part-time employment).
 - Willing to comply with their employer's potential or confirmed COVID-19 incident protocol
 - Agrees to undergo COVID-19 testing per standard of care using an FDA approved method upon the presentation of symptoms indicative of an influenza like illness (if a confirmatory COVID-19 diagnosis is given, participant will be offered to cross-over to HCQ 600 mg qd for 14 days.)
3. Reviews the study and the Informed Consent Form with the subject and obtains informed consent via DocuSign
4. Participant study ID is assigned, and subsequently, randomized into a study arm (HCQ or placebo).

PATCH 2 & 3 TRIAL

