5.0 RANDOMIZATION

[figure not shown]
Randomization will be done using computer generated randomization numbers. Randomization will be stratified by age. Treatment **will start upon receipt of the product by the patient after enrolling in the study, notifying the pharmacy and having the product/placebo sent.**

Blinding: Both sub-studies will have a double-blind placebo-controlled design.

Unblinding: (*See study process flows*)

- For PATCH 2 (Sub-study 1), If patient in PATCH 2 experiences worsening of symptoms, a Co-PI will be notified to take appropriate clinical action. Co-PI can choose to unblind for clinical determinations.
- For PATCH 3 (Sub-Study 2), confirmation of a COVID-19 diagnosis would trigger the unblinding pathway for a participant (for details see *Section 4.0, Participant Registration, PATCH 3 (Sub-Study 2) Participant Procedure*).

Figure 1. Schematic of PATCH 2 and PATCH 3 Study Designs

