8.2 Dose Delays

Major Events are Grade 3 and 4 hematologic and non-hematologic toxicities that are not treatment related. Treatment should be delayed for major events if HCQ may further complicate the non-treatment related event. If a major event requires a delay of treatment, treatment must be delayed until toxicity is resolved (\leq Grade 2 or \leq Baseline). For treatment-related toxicities and major events, if toxicity is not resolved in ≤ 7 days, participant will be taken off treatment unless there is an exception granted by the medical monitor.

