8.5 Hydroxychloroquine Dose Reduction

Any Adverse Event Grade 3 or higher requires HCQ to be withheld. Treatment may be resumed once toxicity is \leq Grade 2 according to the below Dose Reduction Schema (Table 1). If toxicity does not resolve or improve to \leq Grade 2 within 7 days, participant will be withdrawn from active treatment unless granted an exception by the Medical Monitor. Medical Monitor should be notified of all toxicities requiring dose withholding or dose adjustments via email or phone.

Any AE = Grade 2 and **attributed as possibly, probably or definitely related to HCQ** will result in a dose reduction of HCQ as described in Table 1.

If AE remains = Grade 2 following the first dose reduction **and attributed as possibly, probably or definitely related to HCQ** following the second dose reduction, then the participant should discontinue treatment.

No more than 2 dose reductions are allowed. It is recommended that dose reductions occur at a minimum of 48 hours apart.

Table 1: Dose Reduction Schema

Sub-Study	Dose mg/day	First dose reduction	Second Dose reduction
1 (PATCH 2)	400 mg (two tablets) twice daily	400mg (two tablets) once daily	200 mg (one tablet) once daily
2 (PATCH 3)	600 (three tablets) mg daily	400 mg (two tablets) once daily	200 mg (one tablet) once daily

Reported non-serious toxicities attributable to HCQ include nausea, anorexia, vomiting, constipation, diarrhea and rash. For any of these AEs occurring at Grade < 2 , HCQ may be continued and the AE managed with supportive care. For **Any AE** with a Grade ≥ 3 , HCQ will be held until the toxicity improves to \leq Grade 2, after which HCQ may be restarted at a reduced dose as described in Table 1.

Example: Management of diarrhea in randomized subjects

Grade 1: (an increase in stool up to 3 per day) results in no change to HCQ

Grade 2: (an increase in stool up to 4-6 per day) results in a Dose Reduction according to Table 1

Grade 3+: (an increase in stool up to 7 or more per day) results in Withholding of HCQ until AE at Grade level 2 or less, followed by a reduction in dose per Table 1.

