15.2 Response Criteria

PATCH 2 (Sub-Study 1): Measurement of SARS-CoV-2 positivity confirmed by an accepted testing method. Rate of hospitalization will be defined by a hospitalization occurring within 30 days of the date of participant enrollment.

PATCH 3 (Sub-Study 2): Rate of COVID-19 infection will be defined by measurement of SARS-CoV-2 identified by accepted testing methods.

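### Section 12.0 removes participants from the study at an undefined progressive disease, so follow-up for the PATCH 2 30-day hospitalisation endpoint can stop before the event

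*Combined protocol and SAP*

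**What the plan says.** Section 12.0 (Participant Withdrawal) lists reasons for withdrawal. The first is "Progression of Disease: Remove participant from study at the time progressive disease is documented". Others are "Extraordinary Medical Circumstance: If at any time the treating physician feels constraints of this protocol are detrimental" to the participant's health, refusal of treatment, failure to comply with the protocol, and "Delay in treatment > 7 days due to toxicity or ongoing toxicity" of Grade 2 or more after two dose reductions. The section does not say whether outcomes are still collected afterwards.

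Section 15.2 defines the PATCH 2 primary endpoint without reference to drug or study status: "Rate of hospitalization will be defined by a hospitalization occurring within 30 days of the date of participant enrollment".

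Other sections handle the same situations differently:

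- **Worsening illness.** Section 4.0, PATCH 2 step 11, says of a patient still taking part who gets worse: "the participant reports worsening of symptoms related to COVID-19 from baseline, this is reported to the PI for further clinical evaluation". In Section 5.0, if a PATCH 2 patient "experiences worsening of symptoms, a Co-PI will be notified to take appropriate clinical action", and the Co-PI may unblind. Neither passage removes anyone from the study.
- **Toxicity unresolved in 7 days.** In Section 8.2, "participant will be taken off treatment unless there is an exception granted by the medical monitor". In Section 8.5, "participant will be withdrawn from active treatment unless granted an exception by the Medical Monitor". Section 12.0 lists a delay of the same length with no such exception.

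**The concern.** Hospitalisation in PATCH 2 is the end point of a worsening illness. A rule triggered by progression therefore acts on the patients most likely to have the primary event. If staff record progression before admission and follow Section 12.0 literally, those patients leave observation while their 30-day window is still open.

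The primary test uses only about 50 test-positive patients per arm, and Section 16.1 states no allowance for loss. Because the trigger is undefined, different staff may apply it at different points in the illness. At stake are the power of the PATCH 2 comparison and, if loss differs between arms, its error rate.

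**Working it through.** **1. The passages side by side.** Three readings of progression are possible.

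- It means hospital admission. Removal then follows the event and nothing is lost.
- It means worsening before admission. Section 12.0 then ends participation, whereas Sections 4.0 and 5.0 call for review with the patient still in the study, and Section 15.2 still counts the next admission.
- In PATCH 3, it means becoming infected. Section 12.0 then conflicts with Section 4.0, where confirmed cases continue HCQ or are offered cross-over.

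The text does not say which is meant.

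**2. Which routes would still see an admission.** Portal reporting ends after Day 14 (4.0, step 10), and the AE reporting period ends at the last dose (9.2). Against that, AEs unresolved at the end of dosing are followed (9.3) and all SAEs from consent are collected (10.0). Section 10.2 exempts admissions for the target disease unless judged a worsening; a first COVID-19 admission in someone enrolled as not needing hospital would normally be one. The last swab is on Day 29, 30 or 31, with Day 1 the first dose. If dosing starts L days after enrolment, that contact falls L+28 to L+30 days after enrolment. It is at or after day 30 for L ≥ 2, and can be 1 to 2 days early for L = 0 or 1. No readable passage applies these routes to the endpoint or to removed participants.

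**3. The plan's own power (16.1).** Inputs: n = 50 per arm, 70% versus 95% not hospitalised, one-sided α = 0.05.

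Power = Φ[(Δ − z_α√(2p̄q̄/n)) / √(p₁q₁/n + p₂q₂/n)]

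With p̄ = 0.825: √(2 × 0.825 × 0.175/50) = 0.0760, and 1.645 × 0.0760 = 0.125. The denominator is √((0.21 + 0.0475)/50) = 0.0718. So (0.25 − 0.125)/0.0718 = 1.74, and power is 95.9%. Simulation with the three stated boundaries gives 96.8% (pooled z) and 96.3% (log-odds-ratio z). The plan's claim of at least 90% holds as a lower bound.

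**4. Effect of missed admissions (assumed shares).** Let a share m of admissions be missed equally in both arms and counted as non-events. Observed rates become 0.30(1 − m) and 0.05(1 − m). Power by exact binomial enumeration, 50 per arm, rejecting at z ≥ 1.6813:

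| m | Observed rates | Log-odds-ratio z (the plan's statistic; 0.5 added if a cell is zero) | Pooled z |
|---|---|---|---|
| 0 | 30% vs 5% | 96% | 97% |
| 20% | 24% vs 4% | 90% | 93% |
| 25% | 22.5% vs 3.75% | 88% | 91% |
| 50% | 15% vs 2.5% | 65% | 78% |

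Power falls below 90% between 20% and 21% missed for the log-odds-ratio z, and between 27% and 28% for the pooled z. The expected number of placebo admissions is 0.30 × 50 = 15, so this is about 3 to 4 missed. Simulating all three looks changes each entry by less than one percentage point. If removed patients are excluded instead of counted as non-events, pooled-z power is about 93% at 25% and 82% at 50% missed.

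**5. Type I error.** With 30% in both arms and the same final boundary, equal loss of 0 to 50% gives 4.6 to 4.8% (pooled z) and 4.0 to 4.6% (log-odds-ratio z), so there is no inflation.

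**The case against.** The strongest reply is that safety reporting already closes the gap. An event requiring a hospital stay is an SAE, all SAEs from consent are collected, open AEs are followed, and the last swab falls near day 30. This stands in part: many admissions would probably be caught. It does not remove the conflict, because none of these routes is stated to feed the endpoint or to continue for someone removed from the study.

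A reader might infer that 30-day ascertainment is missing from the plan. The documents do not support that. The Appendix 1 and 2 flow charts and some appendix pages could not be read, and Section 12.0 neither requires nor forbids later outcome collection.

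A reader might also infer that the progression rule inflates type I error in favour of HCQ. That does not follow either. With blinding and no treatment effect on the disease, a disease-progression rule gives no reason for unequal loss. Unequal loss would have to come from elsewhere, for example toxicity or compliance withdrawals, and the documents give no shares for these.

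It is also fair to object that better follow-up alone may not be enough. Section 15.1 limits evaluability for the primary outcome to those with at least one continuous week of HCQ, so a participant removed early could still be excluded from the analysis. This is accepted and belongs in the fix.

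**Conclusion.** The inconsistency is real and should be fixed. Section 12.0 removes participants from the study on an undefined trigger and mixes leaving the study with stopping drug, in conflict with Sections 4.0, 5.0, 8.2, 8.5 and 15.2. Confidence is high on the wording conflict. The size of any outcome loss is unknown, because it depends on what progression means in practice and on how many admissions the safety routes recover.

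The power figures are illustrations. They assume the plan's 30% versus 5%, 50 test-positive patients per arm, and equal shares missed and counted as non-events. On those terms the stated 90% survives until roughly 20 to 27% of admissions are missed, depending on the test. Equal loss up to 50% costs power only. Unequal loss could move the one-sided error either way: up if more admissions are missed on HCQ, down if more are missed on placebo.

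**What to change.** - In Section 12.0, separate stopping study drug from leaving the study. State that none of the listed reasons ends outcome follow-up and that only withdrawal of consent does.
- Clarify what progressive disease means in this trial. Reconcile Section 12.0 with Sections 4.0, 5.0, 8.2, 8.5, 9.2, 9.3, 10.0, 10.2, 15.1 and 15.2, without changing any treatment-stopping rule. Section 15.1 must be included, because its one-week rule could otherwise still drop these participants from the primary analysis.
- At the planned Day 15–17 and Day 29–31 test contacts, or by phone if the swab is missed, ask randomised PATCH 2 participants about any hospital admission or death, with dates. Cover at least all test-positives, whatever their drug status. Make the last enquiry no earlier than 30 days after enrolment.
- Report the number with unknown 30-day status by arm.

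The cost is revised wording, one added question at test contacts that are already scheduled, and phone calls to participants who are off drug, miss the swab, or are contacted before day 30. Asking all 500 enrolled would need more calls than asking only the roughly 100 test-positives used in the primary test.

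### Section 12.0 takes participants out of the study, not only off drug, at an undefined disease progression, which could lose PATCH 2 hospitalizations before they are counted

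*Combined protocol and SAP*

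**What the plan says.** **Withdrawal.** Section 12.0 lets investigators end a participant's "participation for any reason, including adverse event or failure to comply with the protocol". It then lists reasons. The progression bullet is worded as an order: "Remove participant from study at the time progressive disease is documented". The other bullets include treatment refusal, non-compliance and "Delay in treatment > 7 days due to toxicity or ongoing toxicity" of Grade 2 or higher after two dose reductions.

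**Endpoint.** Section 15.2 sets the PATCH 2 outcome: "Rate of hospitalization will be defined by a hospitalization occurring within 30 days of the date of participant enrollment". It does not require the patient to be on drug or still on study.

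**Worsening elsewhere.** Item 11 of the PATCH 2 procedure in 4.0 covers "worsening of symptoms related to COVID-19 from baseline, this is reported to the PI for further clinical evaluation". Section 5.0 adds that the "Co-PI can choose to unblind for clinical determinations". Neither mentions removal.

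**Toxicity elsewhere.** For toxicity unresolved after 7 days, 8.2 says the "participant will be taken off treatment unless there is an exception granted by the medical monitor", and 8.5 says the "participant will be withdrawn from active treatment unless granted an exception by the Medical Monitor". Section 8.5 also stops treatment for related Grade 2 events that persist after the second dose reduction, with no exception. Section 8.3, headed ocular toxicity, says without qualification that retinopathy is the only toxicity that requires HCQ to be stopped.

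**The concern.** PATCH 2 enrolls people at home who do not need hospital care and counts how many are later admitted. For such a patient the natural meaning of progression is clinical worsening, and worsening usually comes before admission. A rule that ends study participation at that moment would release the patients most likely to have the primary event. Staff also have two different instructions for the same situation: evaluate and perhaps unblind (4.0, 5.0), or remove (12.0).

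The toxicity reasons raise a similar question. Sections 8.2 and 8.5 end treatment, while 12.0 lists much the same events as reasons to leave the study. At stake are the completeness of the primary endpoint, the power claimed for it and, if losses differ by arm, the validity of the comparison.

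**Working it through.** **1. Is there follow-up after removal?** The relevant sections, side by side:

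- 9.2 ends adverse event reporting at the last dose.
- 9.3 and 9.4 follow events unresolved at the end of dosing until they resolve or stabilize.
- 10.0 collects all serious events after consent, whether or not related. It counts a required hospital stay as serious. After the study period it asks only for events at least possibly related to treatment or participation.
- 10.2 exempts hospitalization for the target disease unless the investigator judges it a worsening.

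These rules may capture some admissions in removed patients. None is day-30 endpoint follow-up, and none says whether a removed patient is counted as hospitalized, not hospitalized or excluded.

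**2. The plan's own power figure.** Inputs from 16.1: 50 test-positive patients per arm, 70% v 95% recovering without hospitalization (30% v 5% hospitalized), one-sided alpha 0.05, stated power at least 90%.

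- Pooled rate (0.30 + 0.05)/2 = 0.175.
- Null SE = √(0.175 × 0.825 × 2/50) = 0.0760.
- Alternative SE = √((0.30 × 0.70 + 0.05 × 0.95)/50) = 0.0718.
- Power = Φ[(0.25 − 1.645 × 0.0760)/0.0718] = Φ(1.74) = 95.9%.

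An exact binomial calculation with the pooled z-test at the final boundary 1.6813 gives 97.0%. A simulation of all three looks (17, 34 and 50 per arm) gives 96.8%. The stated lower bound is met.

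**3. Equal loss in both arms.** Let q be the share of would-be hospitalizations removed before admission. The documents give no q, so these are assumed values. Expected hospitalizations are 50 × 0.30 = 15 on placebo and 50 × 0.05 = 2.5 on HCQ.

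- Excluded, q = 25%: placebo (15 − 3.75)/(50 − 3.75) = 11.25/46.25 = 24.3%; HCQ 1.875/49.375 = 3.8%.
- Excluded, q = 50%: placebo 7.5/42.5 = 17.6%; HCQ 1.25/48.75 = 2.6%.
- Counted as not hospitalized: 22.5% v 3.75% at q = 25%; 15% v 2.5% at q = 50%.

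| q (assumed) | Excluded: exact, final look | Excluded: normal approx. | Counted as not hospitalized: exact, final look | Counted as not hospitalized: normal approx. | Counted as not hospitalized: three-look simulation |
|---|---|---|---|---|---|
| 0 | 97% | 95.9% | 97% | 95.9% | 96.9% |
| 25% | 93% | 90.4% | 91% | 88.1% | 90.6% |
| 50% | 82% | 78.4% | 78% | 71.9% | 77.6% |

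The normal approximation uses alpha 0.05 in a fixed design. The two 0% simulation results (96.8% and 96.9%) differ only by simulation noise.

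**4. Type I error (exact, final look, no true effect).** With removed patients excluded:

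- No loss: 4.8%. Equal loss of 25% or 50% of events in both arms: 4.7% or 4.8%.
- Loss of 5% or 10% of events in the HCQ arm only: 6.1% or 7.6% in PATCH 2 (30% in both arms). In PATCH 3 (10% in both arms, 175 per arm, boundary 1.6664) it is 6.4% or 8.4%.
- Loss of 5% or 10% of PATCH 2 HCQ patients regardless of outcome: 4.7%.

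Inflation therefore needs loss that differs by arm and is tied to the outcome.

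**5. 8.3 against 8.5.** The 7-day rules in 8.2 and 8.5 allow a medical monitor exception, so they can be reconciled with 8.3. The second-reduction rule in 8.5 has no exception and requires a stop for a toxicity other than retinopathy. That is the clear conflict.

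**The case against.** The documents do not say that progression precedes admission. If staff documented it at admission, the event would already have happened and nothing would be lost. The bullet may be text carried over from oncology: 13.1 mentions dose escalations and the job aids mention radiotherapy for CNS metastasis. The COVID-specific instructions for worsening are clear, and the safety rules in step 1 give some route to an admission. All of this stands. It makes event loss a risk and not a certainty, but it does not remove an instruction that staff may follow.

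The loss rates have no source. The exact figures use a pooled z-test at the final look, whereas 16.1 specifies a log-odds-ratio z with interims. At 25% loss the exact power is still above 90%. The one-week evaluability rule in 15.1 may already exclude early progressors. The figures are illustrations only.

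Three stronger readings are tempting:

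- *The plan discards outcomes after withdrawal.* It does not say so. 15.2 is not limited to people on study, and some process-flow figures are not shown.
- *The rule inflates false positives.* It applies to both arms. Inflation appears only in the assumed HCQ-only event losses.
- *PATCH 3 stops looking for infection once drug stops.* The daily record is tied to taking medication, but the weekly portal review, the call-in line and the Day 61-63 tests (4.0 items 7, 8 and 11) are not. There is no case here for extending the daily diary.

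On 8.3, the ocular heading and the operative rules in 8.5 and 12.0 make a staff error unlikely. The contradiction is literal but minor.

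**Conclusion.** The point holds as a conflict in the rules that puts the PATCH 2 primary endpoint at risk; it does not show that the endpoint is damaged. Section 12.0 orders removal from the study at an undefined event and lists toxicity, refusal and non-compliance as reasons for study withdrawal, while 4.0, 5.0, 8.2 and 8.5 call for evaluation or for stopping drug.

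The consequence rests on two assumptions: that progression is read as worsening before admission, and that removed patients are not followed to day 30. Under both, the loss of power depends on an unknown loss rate. It is modest at 25% and takes power below the promised 90% at 50%, whichever way removed patients are counted. The change should be made, with medium confidence in the practical effect. The 8.3 wording is a separate, minor inconsistency that affects none of these figures.

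**What to change.** **Section 12.0.** Replace the progression bullet with stopping study drug if clinically indicated. State that progression, toxicity, treatment refusal and non-compliance end study drug only. State also that hospitalization to day 30 (PATCH 2) and Day 61-63 testing (PATCH 3) are collected in everyone randomised unless consent to follow-up is withdrawn.

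**Section 8.3 (minor).** Reword to: *Retinopathy requires immediate permanent discontinuation, in addition to the stopping rules in 8.2 and 8.5.*

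**Cost.** Wording changes, plus a small amount of extra follow-up of participants who have stopped drug, using contacts and tests already planned.
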